6.4 Planned secondary subgroup analyses

The two populations of women (having primary or secondary prolapse surgery) will be analysed as separate trials as shown above in section 6.1.

Subgroup analyses (separately for the two populations) will explore the effect on prolapse symptoms at 12 months after surgery of:

- 1. mesh kit versus other procedures in those that could have been randomised to mesh kits;
- 2. concomitant continence procedure or not;
- 3. concomitant hysterectomy/cervical amputation/vault procedure or not;
- 4. age (<60 or >=60 years);
- 5. parity; and
- 6. between those having one type of prolapse repair alone (anterior or posterior) versus both.

Heterogeneity of treatment effects amongst subgroups will be tested for using the appropriate subgroup by treatment group interactions.¹¹ Stricter levels of statistical significance (2P<0.01) will be sought, reflecting the exploratory nature of these analyses. All study analyses will be according to a statistical analysis plan that will be agreed in advance by the PROSPECT Steering Committee.

Methodological analyses

The responses from women and their objective clinical findings will provide a rich data source for exploration of the correlation between patient-reported and clinician-observed outcomes, and between prolapse symptoms and their effect on quality of life. This methodological research is intended to advance the controversial field of prolapse outcome measurement, and build upon our existing work in this area.

6.5 Economic issues

The trial will include a formal economic evaluation assessing the costs and cost-effectiveness of the interventions from the perspective of the NHS and from the women and their families. NHS and patient costs will be presented separately. In the base case analysis relative cost-effectiveness will be based upon NHS costs only, as it is the appropriate use of the NHS's budget that the economic evaluation seeks to inform. Nevertheless, the effect of incorporating patient costs will be considered in sensitivity analysis. This wider perspective will also identify the effect of any shifts in the balance of care between the NHS and patients and their families.

6.5.1 Collection of NHS resource utilization data and costs Resource utilization

Data collected will include the resources used for the intervention and the use of primary and secondary NHS services by the women including referral for specialist management. Resource use will be recorded prospectively for every patient within the study.

For the surgical interventions operative details will be recorded at the time of surgery (e.g. time the surgery takes, the time spent in recovery, grade of surgeon and assistant, grade of anaesthetist). These details will be recorded on the theatre form.

A parallel exercise will establish resources used immediately before, during and after (i.e. in recovery) the operation e.g. other staff, consumables (surgical requisites, mesh) and capital (costs associated with using the theatre facilities, costs of using reusable equipment).

The use of secondary care services (e.g. length of hospital stay, outpatient appointments and readmissions) will be recorded on the CRF.

The use of primary care services, including medications will be collected using a health service utilisation patient questionnaire. This questionnaire (the health care utilisation questionnaire) will be organised centrally at the Study Office in Aberdeen and will be administered at baseline, 12, and 24 months post randomisation. This approach will also facilitate long-term follow up, even if participants move.

Costs of intervention

Health service costs incurred as the consequence of the prolapse surgery will be estimated prospectively for every participant in the study. Main areas of costs will be: staffing (gynaecologists and nurses), theatre and hospital resource use, capital costs (buildings and equipment), and consumables (mesh inlays, sutures, mesh kits, catheters, packs etc). NHS costs of other health services used will include:

- Consumables (drugs, pads etc)
- Staff time (GP, nurse, consultants)
- Outpatient visits
- Further hospital admissions (operations for complications, other treatment for complications, repeat prolapse surgery)

Unit costs/prices will be obtained using study specific and published estimates for health care services and/or interventions.

6.5.2 Collection of participant resource utilisation and costs Resource use utilisation data

Participant resource utilisation will comprise three main elements: self purchased healthcare; travel costs for making return visit(s) to NHS health care; and time costs of travelling and attending NHS health care.

- Self-purchased health care is likely to include items such as pads bought by the participant, prescription costs and over the counter medications. Information about these will be collected through the health care utilisation questions (see 6.5.1 above).
- Estimation of travel costs requires information from participants about the number of visits to, for example, their GP or physiotherapist (estimated from the health care utilisation questions) and the unit cost of making a return journey to each type of health care provider (from the Participant Time and Travel Cost Questionnaire).
- The cost of participant time will be estimated in a similar manner. The participant will be asked, in the Participant Time and Travel Cost Questionnaire, how long they spent travelling to and attending their last visit to each type of health care provider. Participants will also be asked what activity they would have been undertaking (e.g. paid work, leisure, housework) had they not attended the health care provider. These data will be presented in their natural units, e.g. hours, and also costed using standard economic conventions, e.g. the Department of Transport estimates for the value of leisure time. These unit time costs, measured in terms of their natural and monetary terms will then be combined with estimates of number of health care contacts derived from the health care utilisation questions.

Administration of time and travel cost questionnaire

The questionnaire eliciting women's time and travel costs associated with accessing and using care will be administered once, at 18 months.

As described above its purpose is to estimate study-specific unit estimates of time and travel costs for individual types of NHS contacts (e.g. outpatient attendances and GP attendances, etc). These unit estimates will then be multiplied by the number of contacts (obtained from the health service utilisation questionnaire) to obtain a total cost for time or travel for that contact. This approach avoids overburdening participants and has been used successfully in many other studies.

6.5.3 Quality of life

A generic instrument (the EQ-5D²⁶) will be used to measure health outcomes. Trial participants will be asked to complete the EQ-5D at baseline and at 6, 12 and 24 months after their prolapse operation. This instrument will provide the quality of life weights to compute the QALYs.

6.5. 4 Cost effectiveness

Effectiveness within the trials will be measured in terms of quality adjusted life years (QALYs) and the subjective prolapse symptom score at 12 months (assessed using data from the POP-SS questions). QALYs will be estimated by combining estimated quantity of life, with quality of life derived from the EQ 5D questionnaire (administered at baseline, 6 and 12 months) and UK tariffs. The estimation of QALYs will take account of the mortality of study participants. Participants who die within the study follow-up will be assigned a zero utility weight from their death until the end of the study follow up. QALYs before death will be estimated using linear extrapolation between the QALY scores at baseline and all available EQ 5D scores up to death. The method of eliciting QALYs described is one commonly adopted in economic evaluation.

The primary analysis is based on the one-year follow-up of the trial and two outcomes have been specified. These are incremental cost per additional woman

cured and incremental cost per QALY. The former outcome has been chosen to facilitate understanding of the findings amongst health care professionals while the second measure, the primary economic outcome, has been chosen to reflect a societal decision-making perspective. The results will be presented as point estimates of mean incremental costs, per QALYs and cost per woman cured or per QALY. Measures of variance for these outcomes are likely to involve bootstrapping estimates of costs, proportion of women cured, QALYs, and incremental cost per additional woman cured and per QALY. Incremental cost-effectiveness data will be presented in terms of cost-effectiveness acceptability curves (CEACs).

Other forms of uncertainty, e.g. concerning the unit cost of a resource, will be addressed using standard deterministic sensitivity analysis. The results of the sensitivity analyses will also be presented as CEACs. Further sensitivity analysis will be conducted to consider the effect of differential timing over which treatments may be given. These data are likely to prove useful for the economic model.

6.5.5 Modelling

While the within study results will prove useful it is important to note that prolapse is a chronic condition and the effects of treatment on costs and outcomes may persist into the future. Therefore, assuming that one intervention is not dominant (less costly but more effective at 12 months), additional useful information for policy makers will be derived from an economic model that considers a longer time horizon. In the model, the findings of the trial will be extrapolated to the patient's lifetime. The model will describe the change in levels of incontinence over the patient's lifetime following the start of treatment. The structure of the model will be developed in collaboration with clinicians and trial collaborators, and parameter estimates for costs and utilities will be derived from the trial data.

In order to extrapolate estimates of cost-effectiveness to a longer time horizon (eg the participant's lifetime) than that considered by the trial, a modelling exercise will be performed. The model will be populated using individual patient data from the study as well as both published and unpublished evidence in the field. The methods used to assemble additional data will follow recognised methodology, which will vary according to the type of parameter, extent of uncertainty and role within the model. Therefore, comprehensive systematic searching will be limited to those parameters to which the results of the model are likely to be particularly sensitive. The modelling exercise will comply with recent recommendations on good practice for modelling and the results will be presented in terms of incremental cost per symptom-free woman and incremental cost per QALY gained.

Estimates of mortality will be based on data from life tables. As the model will be constructed to estimate outcomes both for women having their first prolapse operation, and those having a repeat operation, who are on average 12 years older, mortality rates will be adjusted, where necessary, using relative risks of mortality after prolapse surgery. These data will be obtained from the literature.

Outcomes in the model will be expressed in terms of an incremental cost per QALY. Parameter uncertainty will be integrated by the incorporation of probability distributions into the model and involving Monte Carlo simulation. Other forms of uncertainty such as that associated with choices made about the structure of the model, discount rate, etc., will be addressed though sensitivity analysis. The base case and sensitivity analyses will be presented as CEACs.

Where data allow, the model will be re-estimated for the sub-groups identified above for the within trial analysis. Outcomes in the model will be expressed in terms of an incremental cost per QALY. Parameter uncertainty will be integrated by the incorporation of probability distributions into the model and involve Monte Carlo simulation. Other forms of uncertainty such as that associated with choices made

about the structure of the model, discount rate, etc will be addressed through deterministic sensitivity analysis. The base case, sub-group and sensitivity analyses will be presented as cost and effectiveness plots and, using the net benefit statistic, as CEACs. The model will also be used to identify priorities for further research by identifying threshold values for key parameters (e.g. failure rates) and by investigating the expected value of information.

[figure not shown]
All study analyses, including the within trial, and modeling analyses will be conducted according to an economic analysis plan that will be agreed in advance by the PROSPECT Steering Committee.

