1.2 The questions which this study will address

Principal Objectives

To determine the effectiveness (including safety) and cost-effectiveness of surgical treatment, primarily in terms of improvement in prolapse symptoms, in women having anterior and/or posterior vaginal wall pelvic organ prolapse surgery, in two groups:

(A) In women having a primary prolapse repair, the effects of:

- 1) a standard repair versus a standard repair using a biological graft inlay; and
- 2) a standard repair versus a standard repair using a non-absorbable or combined mesh inlay.

(B) In women having a secondary prolapse repair, the effects of:

- 3) a standard repair versus a standard repair using a non-absorbable or combined mesh inlay; and
- 4) a standard repair versus a mesh kit procedure.

The two groups are being considered independently because different surgical options are considered to be appropriate for clinical reasons.

Secondary Objectives

- to determine the differential effects on other outcomes such as urinary, sexual and bowel function, quality of life, general health, need for secondary surgery and adverse effects;
- to identify possible effect modifiers (eg different types of mesh, concomitant procedures, age, complex prolapse types);
- 7) to establish if the findings of the research, including implications for service delivery, training and introduction of mesh, are generalisable to the NHS.

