1.1 Scale of the problem in the UK and use of NHS resources

Pelvic organ prolapse (POP) is the descent from its normal anatomical position of some of the female genital organs. POP is caused by herniation through deficient pelvic fascia, or due to weaknesses or deficiencies in the ligaments or muscles which should support the pelvic organs. There is little epidemiological research into this condition because it has a variety of presentations and they do not all cause symptoms, particularly in the early stages. ¹⁶ Estimates of the prevalence of prolapse vary from 41% ¹⁷ to 50% ¹⁸ of women over the age of 40 years.

It has been estimated that women have a lifetime risk of 11% of undergoing surgery for urinary incontinence or prolapse and 7% for prolapse alone. The annual incidence of surgery for POP is within the range 15 to 49 cases per 10,000 women years, and it is likely to double in the next 30 years. Little is known about the prevalence and effectiveness of different types of operations, but it is notoriously prone to failure: around 30% of women undergo further operations, the mean time interval to the first secondary operation is about 12 years, and the time interval between subsequent procedures decreases with each successive repair. In addition, repair of one type of prolapse may predispose the women to the development of a different type of prolapse (a new, or de novo prolapse) in another compartment of the vagina due to alteration in the dynamic forces within the pelvis.

Surgery is common. In England and Wales in 2004-2005, 26,947 women were admitted to hospital with a main diagnosis of female genital prolapse, and 28,297 operations were performed (some women had more than one type of prolapse operation). The majority of the operations (93%) were in women having anterior repair (n=8,560), posterior repair (5,406), or both operations (5,654), or with a concomitant uterine prolapse (6,837). Only 7% were in women with vault prolapse (1,840). Assuming a population of about 20 million women in the age group at risk for prolapse surgery (50 to 85 years), the UK operation rate is currently around 14¹⁴ to 16²⁰ women having prolapse operations per 10,000 per year.

The need is likely to increase due to the rising number of elderly women. It has been projected that the number of women in the age group 50 to 85 years (those most likely to need prolapse surgery) will increase by 1.14 million between 2004 and 2014.¹⁵

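### Protocol 6.5.5 says the lifetime economic model will follow incontinence, which contradicts the prolapse objective and the rest of that section

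*Protocol*

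**What the plan says.** Protocol 6.5.5 gives the reason for a model that runs beyond the trial: "prolapse is a chronic condition and the effects of treatment on costs and outcomes may persist into the future". It then says that "the findings of the trial will be extrapolated to the" patient's lifetime, and describes the content in one sentence: "The model will describe the change in levels of incontinence over the" patient's lifetime after treatment starts. The structure is left open: "The structure of the model will be developed in collaboration with clinicians and trial collaborators". On inputs, "parameter estimates for costs and utilities will be derived from the trial data". On outputs, "the results will be presented in terms of incremental cost per symptom-free woman and incremental cost per QALY gained". Later in the section, failure rates are given as an example of a key parameter, and all modelling is placed under an economic analysis plan to be agreed in advance by the Steering Committee.

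The principal objective in Protocol 1.2 covers effectiveness and cost-effectiveness, "primarily in terms of improvement in prolapse symptoms". Protocol 6.2 lists urinary and faecal incontinence as secondary outcomes. It also lists the model's incremental costs, QALYs and cost per QALY among the economic outcome measures. The SAP (Primary Outcomes) refers the cost-effectiveness analysis to the economic analysis plan and says nothing about the model.

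**The concern.** The sentence stands in the analysis section, not in the background, and it names a condition other than the one the trial is about. It does not say whether urinary or faecal incontinence is meant, although both are trial outcomes.

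At stake is the part of the main study's economic evaluation that looks past the follow-up period. According to Protocol Appendix I, section 1.3, the extra purchase cost of mesh arises at the operation: around £200 for an inlay and £400 to £600 for a kit. Much of what could offset or add to that cost comes later. Appendix I, section 1.1, says that "around 30% of women undergo further operations, the mean time interval to the first secondary operation is about 12 years". A model whose only described content is incontinence gives no assurance that these later prolapse events are represented. It also leaves *symptom-free woman*, one of the two result measures in 6.5.5, open to being read as *continent woman*.

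**Working it through.** The plan gives no figure to reproduce, so the check is a comparison of passages.

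1. **What the model follows.** The quoted sentence says incontinence. No other sentence of 6.5.5 in the text supplied says that the model follows prolapse symptoms, recurrence, reoperation or mesh complications over time. One figure in that section is not shown, so this holds for the visible text only.

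2. **What the rest of 6.5.5 describes.**
   - Rationale: prolapse as a chronic condition.
   - Populations: women having a first prolapse operation and women having a repeat one.
   - Key parameter: failure rates.
   - Inputs: trial costs and utilities, with published and unpublished evidence.

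   None of these calls for a model centred on incontinence. The first three point to prolapse.

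3. **Rank of the outcomes.** In Protocol 6.2 the primary clinical outcome is prolapse symptoms on the POP-SS, and incontinence is secondary. Further surgery and mesh erosion or removal are listed there too, so the data for prolapse-based content are already collected.

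4. **Where the model sits in the economic evaluation.** Protocol 6.5.4 bases the primary economic analysis on one-year trial follow-up, with cost per QALY and cost per woman cured. It takes effectiveness from EQ-5D and POP-SS and needs no model. Under 6.5.5 the model is extra information, used when no intervention is dominant.

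5. **Horizon.** Main-study follow-up is 24 months (Protocol section 5), that is 2 years. The mean interval to a first repeat operation is about 12 years. Since 2/12 = 1/6, observation in the main study ends about one sixth of the way to that mean, and within the main study's economic evaluation only the model covers the remainder. Appendix IV, on long-term follow-up, makes repeat prolapse surgery an additional primary clinical outcome, so the plan itself treats it as a central long-term event.

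6. **Mesh complications.** Appendix I, section 1.2.2, quotes erosion rates from the review it cites. Those relevant to the trial arms are 6% for biological and 10% for non-absorbable synthetic mesh. The 1% given there is for absorbable synthetic mesh, which Protocol 3.1 does not offer.

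7. **Definition of symptom-free.** Section 6.5.5 gives none. The SAP (Primary/Secondary Outcomes) uses POP-SS = 0 for the binary part of its model of the 12-month score, as a way of handling many zeros. Under the SAP's Primary Outcomes, missing items score zero unless all seven are missing. A woman who answers one item with *never* and leaves six blank scores 0 + 6 × 0 = 0 and would count as symptom-free.

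**The case against.** The best reply is that this is one loose sentence in a section that is otherwise plainly about prolapse. The structure is expressly left to later work with clinicians and collaborators, so no health states are fixed. Protocol 6.5.1 collects the costs of repeat prolapse surgery and of treating complications, and 6.5.5 takes the model's costs from trial data, so those costs need not be lost. The economic analysis plan may already describe the model correctly.

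Much of this stands, and it limits the point. A reader might infer that the trial cannot answer its cost-effectiveness question. The documents do not support that, because the primary economic analysis does not depend on the model. A reader might also infer that repeat surgery and mesh complications will be left out, or that symptom-free means continent. Neither is stated. Omission is what the sentence gives if followed literally, and an open structure makes it a risk rather than a certainty.

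The reply does not remove the contradiction. Because the structure is open, the one sentence on content is the only visible guide to it. A separate plan that says something different would leave the two documents in conflict.

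**Conclusion.** The sentence is wrong as written and should be corrected. It contradicts the objective in Protocol 1.2 and the rest of 6.5.5. Taken literally, it would rest the lifetime cost per QALY on a secondary outcome. The reach is confined to the lifetime extrapolation, and the one-year within-trial analysis is untouched.

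The size of any error in the cost-effectiveness ratio cannot be computed from the documents, which give no transition rates, utilities or costs of later events. The mesh prices, the 30% and 12-year figures and the 6% and 10% erosion rates show which events matter. They do not give the size of a bias.

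The verdict assumes that the figure not shown in 6.5.5 does not describe the model's content differently. Whether the economic analysis plan already resolves the point cannot be checked.

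**What to change.** In Protocol 6.5.5, replace the reference to levels of incontinence with wording to this effect:

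> Over the woman's lifetime the model will follow prolapse symptoms, recurrence or further prolapse surgery, and mesh complications. Urinary incontinence will be included as one possible consequence affecting cost and utility.

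The detailed structure can stay with the planned collaboration.

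Add that symptom-free refers to prolapse symptoms. Set the exact cut-off in the economic analysis plan. If POP-SS = 0 is chosen there, the plan should say how partly completed questionnaires are handled, given the missing-item rule.

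Check both changes against the economic analysis plan and align the two documents if they differ. The cost is two sentences in the protocol and one cross-check. No new data collection and no change to the SAP's clinical analyses are needed.
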